15.2. SECONDARY EFFICACY

15.2.1. SECONDARY EFFICACY VARIABLES & DERIVATIONS

The following parameters are based on an imputation of CDAI described in Section 15.2.2:

15.2.1.1. CDAI clinical response

The proportion of patients in each treatment group with a clinical response (CDAI decrease of ≥ 70 compared with baseline) will be assessed at Week 24.

The derivation of CDAI decrease is detailed in section 15.1.1. Subjects with a decrease greater or equal to 70 are responders. Other subjects are considered as non-responders.

In addition, RR and risk difference together with 90% and 95% CIs will be presented.

15.2.1.2. CDAI clinical remission

The proportion of patients in each treatment group in clinical remission (CDAI < 150) will be assessed at Week 24.

Subjects with CDAI < 150 at Week 24 will be considered as clinical remission cases.

In addition, RR and risk difference together with 90% and 95% CIs will be presented.

Document: \\ieedc-
vnasc01\BIOSdata\Boehringer_Ingelheim\BI_695501\NVA96252\Biostatistics\Documentation\S
AP\BI1297.4 SAP FINAL v4.0_22MAY2019.docx

Author: Version Number: Final V4.0
Version Date: 22MAY2019

Template No: CS_TP_BS016 Revision 5
Effective Date: 01Apr2018

Reference: CS_WI_BS005

15.2.2. MISSING DATA METHODS FOR SECONDARY EFFICACY VARIABLE

Missing CDAI at Week 24 will be imputed using the combination of NRI and LOCF methods. Only the data up to Week 24, inclusive, will be considered.

The following table details exactly where the NRI / LOCF imputation method will be applied for the sensitivity analysis.

Table 1: Application of LOCF / NRI for the secondary analysis on the FAS

Secondary analysis (FAS)	prior to/on Week 24	
	Discontinued treatment [#]	Did NOT discontinue treatment
CDAI computable using observed data at Week 24	Observed	Observed
CDAI NOT computable using observed data at Week 24	NRI applied	LOCF applied

[#] lost to follow-up (according to eCRF record for “End of Treatment” or “Trial Completion”) is also included here, or patients who took a therapy that may significantly impact efficacy assessment prior to this time-point.

The following steps will be followed:

STEP 1:

Missing CDAI score will be imputed using LOCF method and CDAI will be calculated based on the imputed scores. Last observation will be carried forward as many times as needed.

STEP 2:

NRI principle will be considered at Week 24 as detailed in section 15.1.2.

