5.3. FULL ANALYSIS SET [FAS]

The full analysis set (FAS) will contain all randomized patients who received at least 1 dose of trial medication, and have all efficacy measures relevant for the CDAI, measured at baseline and at least once post-baseline (on Week 4).

For analyses and displays based on FAS, subjects will be classified according to randomized treatment.

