15.1.2. MISSING DATA METHODS FOR PRIMARY EFFICACY VARIABLE

No missing data for the primary analysis endpoint are expected for the FAS, because Week 4 is the first post-baseline visit for efficacy assessment and, in case of discontinuation prior to Week 4, the EoT efficacy assessments should be performed.

The non-responder imputation principle will be followed for the FAS. CDAI evaluation will be set to non-

Document: \\ieedc-vnasc01\BIOSdata\Boehringer_Ingelheim\BI_695501\NVA96252\Biostatistics\Documentation\SAP\BI1297.4 SAP FINAL v4.0_22MAY2019.docx

Author: Version Number: Final V4.0
Version Date: 22MAY2019

Template No: CS_TP_BS016 Revision 5
Effective Date: 01Apr2018

Reference: CS_WI_BS005

responder at Week 4 if the subject:

- discontinues treatment prior to Week 4
- is lost-to-follow-up (according to eCRF record for “End of Treatment” or “Trial Completion”) prior to Week 4

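### SAP 15.2.2 gives no single rule for a missing Week 24 CDAI: Table 1 and STEPS 1–2 differ for dropouts (if STEP 2 is read literally) and for patients who took an efficacy-affecting therapy

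*SAP*

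**What the plan says.** SAP 15.2.2 covers the two Week 24 secondary efficacy endpoints: CDAI response (decrease of at least 70) and CDAI remission (below 150). It opens by saying that a missing Week 24 CDAI is handled by combining NRI and LOCF, with data up to and including Week 24. It then gives two sets of instructions.

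- **Table 1** is introduced with "The following table details exactly where the NRI / LOCF imputation method will be applied for the sensitivity analysis", although its title calls it the secondary analysis. A computable Week 24 CDAI is used as observed. In the row "CDAI NOT computable using observed data at Week 24", patients who discontinued treatment get NRI and the others get LOCF. A footnote adds to the discontinued column patients lost to follow-up and "patients who took a therapy that may significantly impact efficacy assessment prior to this time-point".
- **The steps** follow the table. STEP 1 imputes missing CDAI by LOCF without exception: "Last observation will be carried forward as many times as needed". STEP 2 reads "NRI principle will be considered at Week 24 as detailed in section 15.1.2".

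SAP 15.1.2, the target of that reference, says "The non-responder imputation principle will be followed for the FAS" and lists two triggers: the patient "discontinues treatment prior to Week 4", or is lost to follow-up before Week 4. It has no therapy trigger and no condition that the CDAI be missing.

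Three other places bear on Week 24:

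- Protocol 7.5.1 leaves the handling of missing secondary data to the SAP. It also says that a Week 4 non-responder stays a non-responder at every later time point.
- SAP 15.1.1 sets the CDAI change to zero when a post-baseline value is missing.
- SAP 15.2.1.1 refers to 15.1.1 for deriving the decrease at Week 24.

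**The concern.** A programmer who works from Table 1 and one who works from the steps can classify the same patient differently. The patients at issue are those who enter maintenance, then drop out or take an efficacy-affecting therapy, and have no Week 24 CDAI.

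Such patients can exist. SAP 6.3 files early-termination data under the End-of-Treatment visit, and 6.4 does not re-window visits, so a dropout who is not followed further has no Week 24 value.

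Only Week 4 responders enter maintenance (SAP 3.1), and the FAS requires a Week 4 CDAI (SAP 5.3). If Week 4 is the last CDAI, the carried value is therefore a response by the entry rule. The literal steps would then count a patient who stopped treatment as a Week 24 responder, where Table 1 counts a non-responder.

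**Working it through.** **Step 1. Set the rules side by side.** SAP 15.2.2 states no figure to reproduce, so the check starts with the text. Events below are after Week 4 and before Week 24.

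| Patient | Week 24 CDAI | Table 1 | Steps, 15.1.2 dates taken literally | Steps, Week 24 timing, missing CDAI only |
|---|---|---|---|---|
| Discontinued or lost | observed | Observed | Observed | Observed |
| Discontinued or lost | missing | NRI | **LOCF** | NRI |
| Took efficacy-affecting therapy | observed | Observed | Observed | Observed |
| Took efficacy-affecting therapy | missing | NRI | **LOCF** | **LOCF** |
| None of these | observed | Observed | Observed | Observed |
| None of these | missing | LOCF | LOCF | LOCF |

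The literal reading departs from Table 1 in two rows. The reading with Week 24 timing departs in one, the therapy takers, because 15.1.2 has no therapy trigger. Timing also differs at the edge: the Table 1 header includes events on Week 24, while its footnote and the 15.1.2 triggers say only *prior to*.

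**Step 2. Which value is carried.** It need not be Week 4. CDAI is also taken at Week 12, and early discontinuers should have an End-of-Treatment visit with a CDAI (Protocol Flow Chart B). A later value may or may not be a response. Let s be the share of carried values that are responses; s = 1 is the upper bound.

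**Step 3. Size under the literal reading.** Inputs: 65 per arm and 80% Week 4 response (Protocol 7.7). Assumptions: d, the share of maintenance entrants who drop out with no Week 24 CDAI, and s.

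- One patient: 1/65 = 1.54 points of an arm's rate.
- Entering maintenance: 65 × 0.80 = 52 per arm. The other 13 are Week 4 non-responders; a carried Week 4 value leaves them non-responders under either rule.
- Affected: 52 × 0.05, 0.10, 0.15 = 2.6, 5.2, 7.8 patients.
- Literal rate minus Table 1 rate = 0.80 × d × s. With s = 1: 4.0, 8.0, 12.0 points. With s = 0.5: 2.0, 4.0, 6.0 points.
- At the pooled historical rate of 54.1% (Protocol Appendix 10.3), with s = 1: 2.7, 5.4, 8.1 points.

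**Step 4. Relative risk.** Equal dropout and equal response leave RR at 1.00. Now assume 10% dropout on BI 695501 and 5% on Humira, with response r among those retained.

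- Table 1: 0.90/0.95 = 0.947.
- Literal: RR = (0.90r + 0.10s)/(0.95r + 0.05s). For r = 0.6, 0.7, 0.8 this is 1.032, 1.021, 1.012 with s = 1, and 0.992, 0.986, 0.981 with s = 0.5.

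The effect on remission is smaller, because a carried Week 4 response need not be below 150.

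**The case against.** The best defence is that Table 1 is plainly meant to govern. Its introduction claims to show exactly where each method applies. STEP 2 names Week 24, so it can be read as borrowing the NRI principle from 15.1.2 and moving the time point. Taken literally, the Week 4 dates would remove every later dropout from Table 1's NRI cell. The steps would then be only an order of execution: LOCF first, NRI overwriting it. For therapy takers, Protocol 7.5.1 includes major therapy deviations in its own definition of NRI, and SAP 3.3 plans no change from the protocol.

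Much of this stands. Table 1 is the probable intention, and under that reading dropouts before Week 24 are handled consistently. Two things remain. The therapy trigger has to be inferred, because 15.1.2 omits it and the protocol's version is tied to the primary endpoint assessment. The sentence that gives Table 1 its authority names a sensitivity analysis, and nothing ranks the table above the steps.

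A reader might infer that discontinuers with an observed Week 24 CDAI also conflict, since 15.1.2 has no missing-data condition, and hence that no reading of STEP 2 treats dropouts as Table 1 does. The documents do not support this: 15.2.2 is about missing CDAI, so STEP 2 need not touch an observed value.

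**Conclusion.** SAP 15.2.2 is internally inconsistent. Followed as written, the steps can carry forward a response for a patient whom Table 1 makes a non-responder. With Week 24 timing and the section's missing-data scope, the conflict narrows mainly to therapy takers with no Week 24 CDAI.

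The size is unknown because the documents give no dropout or therapy rates. The range of 4–12 points is an upper bound. It rests on the literal reading, 80% Week 4 response, an assumed 5–15% dropout with no Week 24 CDAI, and every carried value being a response. If half are responses, it is 2–6 points.

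A reader might infer that the rule reverses the treatment comparison. In the example with unequal dropout, RR passes 1 only if every carried value is a response; with half it stays below 1. The primary endpoint is not affected, and both Week 24 endpoints are interpreted descriptively.

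Two further gaps have to be closed if Table 1 is to govern:

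- Its Observed cell could count a Week 4 non-responder as a Week 24 responder, against Protocol 7.5.1. This would be rare, but Protocol 3.3.4.1 does ask for efficacy follow-up of patients off treatment where possible.
- The zero-change rule of 15.1.1 is a third possible treatment of a missing value. SAP 15.2.1 bases the Week 24 variables on the 15.2.2 imputation, which suggests that imputation comes first, but the order is not stated.

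**What to change.** Amend SAP 15.2.2 as follows:

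1. State that Table 1 governs the secondary analysis, and change *sensitivity analysis* to *secondary analysis* in its introduction.
2. Replace STEP 2 with a self-contained rule: a patient who, before or on Week 24, stops treatment, is lost to follow-up or takes a therapy covered by the Table 1 footnote, and whose Week 24 CDAI cannot be computed from observed data, is a non-responder and a non-remitter.
3. Limit the LOCF in STEP 1 to patients with none of these events, and give the footnote the same before-or-on timing as the Table 1 header.
4. Add the Protocol 7.5.1 rule that Week 4 non-responders remain non-responders at all later time points, and let it override the Observed cell for response.
5. State that the zero-change rule of 15.1.1 is not applied at Week 24 before the 15.2.2 imputation.

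The cost is five wording changes and the programming of a derivation that is already planned; no new data are needed. The downside is that Week 24 rates may be somewhat lower than under the literal steps.

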15.2.3. ANALYSIS OF SECONDARY EFFICACY VARIABLES

Secondary efficacy endpoints will be presented with descriptive statistics for FAS and PPS2. The relative risk of the proportions will be computed and presented together with its 90% and 95% CI and risk difference and interpreted in a descriptive manner.

Document: \\ieedc-vnasc01\BIOSdata\Boehringer_Ingelheim\BI_695501\NVA96252\Biostatistics\Documentation\SAP\BI1297.4 SAP FINAL v4.0_22MAY2019.docx

Author: Version Number: Final V4.0
Version Date: 22MAY2019

Template No: CS_TP_BS016 Revision 5
Effective Date: 01Apr2018

Reference: CS_WI_BS005

Document: \\ieedc-
vnasc01\BIOSdata\Boehringer_Ingelheim\BI_695501\NVA96252\Biostatistics\Documentation\S
AP\BI1297.4 SAP FINAL v4.0_22MAY2019.docx

Author: Version Number: Final V4.0
Version Date: 22MAY2019

Template No: CS_TP_BS016 Revision 5
Effective Date: 01Apr2018

Reference: CS_WI_BS005

Document: \\ieedc-
vnasc01\BIOSdata\Boehringer_Ingelheim\BI_695501\NVA96252\Biostatistics\Documentation\S
AP\BI1297.4 SAP FINAL v4.0_22MAY2019.docx

Author: Version Number: Final V4.0
Version Date: 22MAY2019

Template No: CS_TP_BS016 Revision 5 Reference: CS_WI_BS005
Effective Date: 01Apr2018

16. SAFETY OUTCOMES

All outputs for safety outcomes will be based on the SAF for overall and Period output.

There will be no statistical comparisons between the treatment groups for safety data, unless otherwise specified with the relevant section.

Safety will be assessed as a secondary objective in this trial.

The safety endpoints considered as secondary endpoints are defined as:

- Proportion of patients with AEs, SAEs, and AESIs (e.g., serious infections)
- Proportion of patients with infections/serious infections (seriousness of infection defined as requirement of i.v. antibiotics for treatment and/or meeting seriousness criteria to be qualified as an SAE)
- Proportion of patients who experience hypersensitivity reactions
- Proportion of patients who experience DILI (Drug Induced Liver Injury)
- Proportion of patients with injection-site reactions

Another safety endpoint is the proportion of patients who discontinue due to drug-related AEs and AESIs (e.g., serious infections and allergic reactions).

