4.1.4 Drug assignment and administration of doses for each patient

Each patient will receive 160 mg (loading dose) of BI 695501 or EU-approved Humira at the Baseline Visit (Day 1) followed by 80 mg of BI 695501 or EU-approved Humira 2 weeks later (Day 15/Week 2), and then 40 mg of BI 695501 or EU-approved Humira at Week 4 (primary endpoint).

At Week 4 (Day 29), patients achieving a clinical response (defined as a decrease in CDAI \geq 70) will continue receiving their randomized treatment (40 mg BI 695501 or EU-approved Humira every 2 weeks) in a blinded fashion. The hematocrit value required to determine CDAI score at Week 4 will be assessed locally and confirmed via central laboratory

Boehringer Ingelheim		12 Dec 2017
BI Trial No.: 1297.4		
c09542349-05	Trial Protocol	Page 34 of 93

assessment. At Week 24, patients originally randomized to EU-approved Humira will switch to receive 40 mg BI 695501 every 2 weeks. All patients will then continue to receive BI 695501 at the same dose until Week 46.

Patients not achieving a clinical response at Week 4 will not receive any further treatment with trial medication, but will be followed up for safety after 10 weeks (Safety Follow-up Visit).

Prefilled syringes will be used for the administration (see Section 4.1.1) and all patients will receive their injections at the trial site throughout the trial until Week 22, and BI 695501/EU-approved Humira will be administered by a dedicated, unblinded member of trial personnel (third party blinding). From Week 24 onwards, when all patients will be receiving BI 695501when all patients will be receiving BI 695501, any suitably trained trial personnel may administer the medication to the patient. However, patients and other trial personnel must remain blinded with respect to the initial assignment to EU-approved Humira or BI 695501.

After the first injection in the induction period (Visit 2) and the injection at Visit 14 (when patients originally randomized to EU-approved Humira will switch to receive BI 695501), patients will remain at the clinical site for at least 1 hour for observation of any AEs.

Dose modification is not permitted during this trial. If a patient misses a dose of trial medication then the dose should be administered as soon as possible, in accordance with the visit schedule presented in Flow Chart A and Flow Chart B.

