5.5. SAFETY ANALYSIS SET [SAF]

The safety analysis set (SAF) will contain all subjects in the RND set who receive at least one dose (full or partial) of trial medication.

If there is any doubt whether a subject was treated or not, they will be assumed treated for the purposes of analysis.

For analyses and displays based on SAF:

- In case the subject was fully incorrectly treated, the subject will be classified according to treatment received
- In case the subject was partially incorrectly treated, the subject will be classified according to treatment

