16.1.1. ADVERSE EVENT SPECIFIC DERIVATION

16.1.1.1. Treatment Emergent Adverse Event

Treatment-Emergent Adverse Events (TEAEs) are defined as AEs that started or worsened on or after the first dose of trial medication and prior to the last date of trial medication + 10 weeks (70 days) inclusive.

There are two specific periods of interest:

Period 1 Treatment-Emergent Adverse Events (P1 TEAEs) are defined as AEs that started or worsened on or after the first dose of trial medication and prior to the date of Week 24 visit or within 10 weeks (70 days, inclusive) after the last dose of IMP for patients who discontinued the treatment before Week 24.

Period 2 Treatment-Emergent Adverse Events (P2 TEAEs) are defined as AEs that started or worsened on Week 24 visit and prior to or on the Week 56 visit or within 10 weeks (70 days, inclusive) after the last dose of IMP for patients discontinuing treatment prior to Week 46.

Non-TEAEs will be classified as "Screening" if AE start date is strictly prior to the first injection date. Non-TEAEs will be classified as "Post treatment" if AE start date is strictly after the last injection date + 70 days.

See APPENDIX 2 for handling of partial dates for AEs. In the case where it is not possible to define an AE as treatment-emergent or not, the AE will be classified by the worst case, i.e., treatment-emergent in the period of the last injection of trial medication.

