16.1.2. ALL TEAEs

Number of subjects, percentages, and number of events overall and for period 1 and period 2 will be presented by SOC and PT and also broken down further by maximum intensity and relationship to trial medication.

Periods for TEAE's:

Period 1	Visit date within 
 • [first injection date; Week 24 Visit] or • [first injection date; last injection date + 10 weeks (70 days)] (for patients that discontinued the treatment before week 24)].
Period 2	Visit date within 
 • [Week 24 Visit; Week 56 Visit[or • [Week 24 visit; last injection date + 10 weeks (70 days)] (for patients that discontinued the treatment before week 56)].

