gunit = pct
cback = white
colors = (black)
hby = 2.4
ftext = "TimesRoman"
htext = 2.5;
```

HEADER INFORMATION

Headers should be defined as follows:

- The header should be placed at the top of the page (same place on each page) regardless of the size or orientation of the table or listing
- The customer name and protocol number should appear in row 1, left-aligned
- The output identification number should appear in row 2, left-aligned
- The output title should start in row 2 after output identification number separated by a double dot, left-aligned
- The output population should appear in row 2 after output title separated by a dash, left-aligned. The population should not be spelled out in full, e.g. FAS in preference to Full analysis set.
- Row 3 should be a continuous row of underscores ('_') (the number of underscores should equal the linesize)
- Row 4 should be a blank line
- Mixed case should be used for titles
- The output titles should be designed so that they are arranged consistently through all outputs. For example, content (e.g., Vital Signs) followed by metric (e.g., Change from Baseline) e.g. Vital Signs – Change from Baseline.
- Titles should not contain quotation marks or footnote references
- The column headings should be underlined with a row of underscores ('_')
- Column headings spanning more than one column should be underlined and have underscores on either side of the title and should be centered
- Column headings containing numbers should be centered
- Column headings should be in sentence case
- In general, the population count should appear in the column header in the form “(N=XXX)”
- “Statistic” should be the column header over n, Mean, SE, n (%) etc.
- As a rule, all columns should have column headings.

Document:	\\ieedc-vnasc01\BIOSdata\Boehringer_Ingelheim\BI_695501\NVA96252\Biostatistics\Documentation\SAP\BI1297.4 SAP FINAL v4.0_22MAY2019.docx		
Author:	Version Number:	Final V4.0	
	Version Date:	22MAY2019	
Template No:	CS_TP_BS016	Revision 5	Reference: CS_WI_BS005
Effective Date:	01Apr2018		

TABLE AND LISTING OUTPUT CONVENTIONS

General:

- The first row in the body of the table or listing should be blank
- The left hand column should start in column 1. No indenting or centering of the output should occur.
- Rounding should be done with the SAS function ROUND, if no further specification.
- Numbers in tables should be rounded, not truncated, if no further specification.
- Alphanumeric output should be left aligned.

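### Period 2 safety percentages are based on the whole safety set, so Week 4 non-responders and patients who stop before Week 24 dilute them

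*SAP*

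**What the plan says.** SAP section 16 sets the population for every safety table, by period as well as overall: "All outputs for safety outcomes will be based on the SAF for overall and Period output". Under SAP 5.5 the SAF "will contain all subjects in the RND set who receive at least one dose (full or partial) of trial medication"; nothing in that definition refers to Week 24. The sets counted in SAP section 9 are ENR, RND, FAS, PPS, PPS2 and SAF. PPS2 is specific to Week 24 but serves efficacy.

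Protocol 4.1.4 fixes who continues: "Patients not achieving a clinical response at Week 4 will not receive any further treatment with trial medication". SAP 16.1.1.1 defines Period 2 events as "AEs that started or worsened on Week 24 visit and prior to or on the Week 56 visit", with a second limb of 70 days after the last dose for patients who stop before Week 46. Its Period 1 definition keeps the 70-day tail of anyone who stops before Week 24 in Period 1.

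The outputs follow in SAP 16.1.2: "Number of subjects, percentages, and number of events overall and for period 1 and period 2 will be presented by SOC and PT". Discontinuations (16.1.3), serious events (16.1.4), non-serious terms above 5% (16.1.5) and injection-site reactions (16.1.7.5) are also planned by period. Appendix 1 gives the default N: "In general, the population count should appear in the column header". It also lets a table divide by another count if a row or footnote identifies it.

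**The concern.** The trial selects at Week 4, so the patients present in Period 2 are a subset of those dosed. A percentage with the SAF count as denominator answers how many of all patients ever dosed had an event after Week 24. It does not answer how often events occur in patients treated after Week 24. The second question is the relevant one: protocol 2.1 says the trial addresses switching, and protocol 3.2 says safety will be assessed in long-term treatment and after the switch. Period 2 is where a reader will look for that. Percentages that are too low make post-switch safety look better in both arms, and can take terms out of the table that applies the 5% cut-off.

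**Working it through.** **Inputs from the documents.** 65 patients per arm and 80% Week 4 response in both arms (protocol 7.7). Scenario of 75% (BI 695501) versus 85% (Humira) response (protocol Table 7.7: 1). Week 2 = Day 15, Week 4 = Day 29, Week 24 = Day 169 (flow charts). Window of 70 days after the last dose (SAP 16.1.1.1).

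**Assumptions, not in the documents.** q = 30% true incidence among patients who enter Period 2; s = retention of responders from Week 4 to Week 24, taken as 1.0, 0.9 and 0.8.

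**Planning figure.** The half-width of the 90% interval for a difference at 80%/80% and 65 per arm is 1.645 × √(2 × 0.80 × 0.20 / 65) = 0.1154. This matches the stated 0.115, so 65 per arm and 80% are the right planning inputs.

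**Can these patients have a Period 2 event?**
- Non-responder, last dose Day 15: 15 + 70 = Day 85. Even with a dose on Day 29: 29 + 70 = Day 99. Both fall before Day 169, so the answer is no on any reading.
- Patient who stops later but before Week 24: the Period 1 definition in SAP 16.1.1.1 places the 70-day tail in Period 1. For a last dose at Week 22 (Day 155) that tail runs to Day 225, past Day 169. The second limb of the Period 2 definition, read literally, could claim the same days. The two limbs need to be made exclusive.

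**Dilution.** With r the Week 4 response, reported percentage = q × r × s.

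| r | s | At risk of 65 | 30% is reported as |
|---|---|---|---|
| 80% | 1.0 | 52 | 24.0% |
| 80% | 0.9 | 47 | 21.6% |
| 80% | 0.8 | 42 | 19.2% |

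The fraction not at risk is 1 − r × s, so at least 20% when r = 80%. It grows if response is lower. At the pooled historical 54.1% in protocol Appendix 10.3, which the protocol does not use for sizing, 30% would read 0.541 × 30% = 16.2% before any attrition.

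**Display cut-off.** SAP 16.1.5 shows terms strictly above 5% in at least one arm. If the cut-off is applied within Period 2, a term seen in 3 of 52 at-risk patients is 5.8%. Over 65 it is 3/65 = 4.6%, and the term is not displayed unless the other arm exceeds 5%. It would still appear in the full table of SAP 16.1.2.

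**Between arms.** With equal q in both arms, the ratio of reported percentages is (r × s in BI 695501) / (r × s in Humira). At 80%/80% and equal retention it is 1.00. At 75% versus 85% and equal retention it is 0.75/0.85 = 0.88; with q = 30% and s = 1.0 the percentages are 22.5% and 25.5%.

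**With at-risk patients as N**, the reported percentage equals q and the ratio is 1.00 whenever q is equal in the two arms.

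**The case against.** The best counter-argument is that the SAP names an analysis set and does not spell out a Period 2 denominator. Appendix 1 permits another count, and SAP section 8 leaves table content to templates that are not in the public text. SAP 5.5 is also incomplete there. This stands in part: use of the SAF count is a strong inference, not a certainty. But section 16 names Period output explicitly, the default N is the population count, and no visible passage directs a different one. The correct denominator should not rest on an unstated choice that departs from the written rule.

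Also fair: SAP section 13 reports the proportion treated at each visit by arm, so a careful reader could rescale the percentages. That limits the harm but does not replace a correct table.

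A reader might go further and infer that a Week 4 efficacy difference carries over into the safety comparison and makes the less effective product look safer. The documents do not support that as a general claim. Every patient receives BI 695501 from Week 24, so the contrast is continued versus switched treatment. The expected distortion is zero at the planned 80%/80% response with equal retention. Protocol 7.3.4 plans adverse-event risk ratios and differences for the overall population, and the SAP 16.1.1.2 code tabulates an overall event variable. Safety is descriptive. The effect is also small against noise: at q = 30% and s = 0.9, the 75%/85% scenario gives 20.3% versus 23.0%, a ratio of 0.88 with an approximate 95% interval of 0.46 to 1.70 at 65 per arm.

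**Conclusion.** The point holds as one about dilution. The written rule puts patients who cannot have a Period 2 event into the Period 2 population. With the default N, Period 2 percentages are understated by at least a fifth in relative terms at the planned response, and by more with attrition. This rests on the SAF count being the denominator and on the protocol's 80% response; the 30% incidence and 10-20% attrition only illustrate the size.

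The side-by-side arm percentages are affected only if Week 4 response or later retention differs between arms, by a factor of 0.88 in the protocol's 75% versus 85% scenario. No type I error rate is involved. It should be corrected because Period 2 carries the switching question and the change is small.

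**What to change.** 1. Add to SAP 5.5 a Period 2 safety set (for example SAF2): SAF subjects with at least one dose of trial medication at or after the Week 24 visit.
2. Reword SAP section 16 so that overall and Period 1 output stay on the SAF and Period 2 output uses SAF2 with its N shown. State that the 5% cut-off in 16.1.5 uses the same N, as would any Period 2 risk ratio or difference if one is produced.
3. Align the Period 2 windows in SAP 16.1.1.1, 16.1.2 and 16.1.7.5 with this set. Their end points and discontinuation limbs differ now (before Week 46 in one, before Week 56 in the others). Events of patients who stop before Week 24 should stay in Period 1 only, so that no Period 2 event falls outside its denominator.
4. Footnote that the set is selected after randomisation: it compares continued with switched treatment among Week 4 responders still on treatment, and is not a fully randomised comparison.

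The cost is one population flag and a few sentences. The downside is a smaller, selected N (about 42 to 52 per arm at 80% response) and higher displayed percentages. The full-SAF overall tables are unchanged.
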